3.3.1 Nasal polyp score

The total NPS is the sum (maximum 8) of the right and left nostril scores, as evaluated by nasal endoscopy and the left and right score will be based on central read with scale from 0 to 4 as listed in Table 6. The total NPS and the changes from baseline to each post-baseline value will be calculated.

Table 6 Endoscopic nasal polyp score

Polyp score	Polyp size
0	No polyps
1	Small polyps in the middle meatus not reaching below the inferior border of the middle turbinate
2	Polyps reaching below the lower border of the middle turbinate
3	Large polyps reaching the lower border of the inferior turbinate or large polyps of score 2 with additional large polyps medial to the middle turbinate
4	Large polyps causing complete or near-complete obstruction of the inferior nasal cavity i.e. touching the floor of the nose

In addition, the NPS response will be derived as mentioned in Section 3.1.5, respectively. A patient will be classified as a responder at the time point of interest if the change from baseline

in total NPS is ≤ -1 (improvement by at least 1 score) at that time point. A 1-grade reduction in bilateral nasal polyp burden has been used in clinical trials of mometasone furoate nasal spray (Stjarne et al 2006) and sinus implants (Kern et al 2018) for NP.

3.3.2 Nasal blockage score

The NBS is an item in the NPSD. Patients were asked to rate the severity of their worst nasal blockage over the past 24 hours using the following response options: 0 – none; 1 – mild; 2 – moderate; 3 – severe. The NBS and the changes from baseline will be summarised every two weeks (bi-weekly). Baseline NBS is defined in Section 3.1.3 and bi-weekly mean will be calculated if at least 8 days in each 14-day period have evaluable data; otherwise, the bi-weekly mean is set to missing.

A responder definition of change in bi-weekly NBS ≤ -1 is based on the global study D3252C00001 (Shih et al 2023). NBS responder analysis will be conducted as described in Section 3.1.5.

3.4 Key secondary efficacy variables

According to the SoA Table 2 and Table 3 in the CSP, key secondary efficacy assessments will be collected during the DB period only. Therefore, derivation of relevant endpoints applies to the DB period and will be reported at the primary DBL.

3.4.1 Difficulty with sense of smell (DSS) score

The DSS is a key secondary endpoint and will be captured by an item in the NPSD. Patients are asked to rate the severity of their worst difficulty with sense of smell over the past 24 hours using the following response options: 0–none; 1–mild; 2–moderate; 3–severe. The DSS and the changes from baseline will be summarised every two weeks (bi-weekly). Baseline will be the average of daily responses from Day –13 to Day 1 (as defined in Section 3.1.3). Bi-weekly mean of DSS will be calculated if at least 8 days in each 14-day period have evaluable data; otherwise the bi-weekly mean is set to missing.

3.4.2 Sinus CT: Lund-Mackay score

The CT data will come from blinded central reader(s), and it will be performed at V2 (Week -2) and at EoDB (Week 56), or IPD or prior to a surgery for CRSwNP if at least 16 weeks passed since the previous CT scan.

The LMS evaluates the patency using a 0-2 scale (0 – no abnormality; 1 – partial opacification; and 2 – total opacification) of each sinus (maxillary, anterior ethmoid, posterior ethmoid, sphenoid, and frontal sinus on each side). The ostiomeatal complex on each side is graded as 0 – not occluded or 2 – occluded. The total CT score is the sum of the scores from all the sinus and ranges from 0 to 24. The total CT score based on LMS will be calculated for the observed values and the changes from baseline at each time point.

3.4.3 Health related quality life: SNOT-22 score

The SNOT-22 is a condition specific HRQL assessment which captures patient-reported physical problems, functional limitations, and emotional consequences of sinonasal conditions. Patient-reported symptom severity and symptom impact over the past 2 weeks are captured via a 6-point scale (0 – no problem to 5 – problem as bad as it can be). The total score is the sum of item scores and has a range from 0 to 110 (higher scores indicate poorer outcomes). The total score and the changes from baseline will be calculated.

A response to SNOT-22 total score will be defined as changes from baseline ≤ -8.90 at the time point of interest. Responder analysis will be conducted according to the approach mentioned in Section 3.1.5.

3.5 Other secondary efficacy variables

According to the SoA Table 2 and Table 3 in the CSP, secondary efficacy assessments will be collected during the DB period only, except that surgery and SCS use for CRSwNP will be further collected during the OLE period.

3.5.1 Time to the first surgery and/or SCS use for CRSwNP

The time to the first surgery for CRSwNP during the DB period will be evaluated for all patients in the PFAS and it is calculated as follows:

Time to the first surgery for CRSwNP = Start date of the first surgery for CRSwNP – date of randomisation + 1

Time to first SCS use for CRSwNP and time to first SCS use or surgery for CRSwNP will be evaluated using the similar approach as time to first surgery for CRSwNP. Namely,

Time to the first SCS use for CRSwNP = Start date of the first SCS use for CRSwNP – date of randomisation + 1

Time to first surgery and/or SCS use for CRSwNP = earlier date of (start date of first surgery for CRSwNP, start date of first SCS use for CRSwNP) – date of randomisation + 1

For patients who do not undergo any surgery or do not experience any SCS use for CRSwNP, the time to the event will be censored at the date of first OLE dose (for those who entered the OLE right after DB completion), or the date of Week 56 Visit (for those who did not enter the OLE after DB, or those who entered DB follow-up period per CSP v1.0 and v2.0), or at the time point after which a surgery or SCS use could not be assessed (for patients discontinued before Week 56 Visit).

The time to recorded decision time to have surgery for CRSwNP will be a supportive endpoint and derived similarly.

3.5.2 SCS use for CRSwNP and proportion of surgery for CRSwNP

The following variables will be summarized during the DB period for all patients in the PFAS (reported at the primary DBL), and during the OLE period for all patients in the OLE analysis set (reported at the final DBL).

- Proportion of patients who had surgery for CRSwNP
- Proportion of patients who use SCS for CRSwNP
- Proportion of patients who had surgery or use SCS for CRSwNP
- The number of courses of SCS for CRSwNP: noted an SCS course can be considered as a new course if the start date is preceded by at least 7 days after the end date of the last SCS course for CRSwNP (i.e. start date of the new course - end date of the last course > 7)
- Total dose of SCS for CRSwNP (converted to prednisolone equivalents)
- Total duration of SCS use for CRSwNP

3.5.3 Nasal polyposis symptom diary (NPSD)

Patients will complete the NPSD each morning. Patients are asked to consider their experience with NP over the past 24 hours when responding to each question and report the severity of each symptom at its worst using a 4-point rating scale (0–none; 1–mild; 2–moderate; 3–severe). Questions to capture patient-reported difficulty with sleep and daily activities due to nasal symptoms use the same rating scale. A TSS will be calculated by taking the sum of the first 8 items in the NPSD.

Bi-weekly mean of each item in the NPSD and TSS, as well as the change from baseline in the bi-weekly mean will be calculated. Bi-weekly mean of each item in the NPSD will be calculated if at least 8 days in each 14-day period have evaluable data; otherwise the bi-weekly mean is set to missing.

3.5.4 University of Pennsylvania smell identification test score

The UPSIT is quantitative test of olfactory function which uses microencapsulated odorants that are released by scratching standardised odour-impregnated test booklets. Four booklets each with 10 odorants each are used for the test. Patients are asked to identify the odour using multiple choice format which lists different possibilities. The test is forced choice, i.e., the patient is required to mark one of the four alternatives even if no smell is perceived. Scores are based on number of correctly identified odours (score range 0 to 40). The UPSIT smell test will be performed in all countries except Thailand and Vietnam. The UPSIT total score and the changes from baseline will be calculated.

The olfactory diagnosis will be classified based on the test scores by gender (male vs female) as listed in [Table 7](#). The categories of Probable Malingering (UPSIT score 0 - 5) and Total Anosmia (6-18) have been combined into a single Anosmia category. Presenting a combined category of anosmia is a conservative approach and ensures anosmia events will not be underreported. This is also consistent with the approach taken in other Phase III clinical trials such as D3252C00001 (OSTRO) and ([Bachert et al, 2019](#)).

Table 7 UPSIT olfactory diagnosis

Olfactory diagnosis	Test scores	
	Male	Female
Anosmia	00 – 18	00 – 18
Severe microsmia	19 – 25	19 – 25
Moderate microsmia	26 – 29	26 – 30
Mild microsmia	30 – 33	31 – 34
Normosmia	34 – 40	35 – 40

3.5.5 Sinus CT: sinus severity score

Quantitative assessment of sinus CT image data will be used to derive an objective measure of sinus disease burden called sinus severity score ([Pallanch et al 2013](#)), defined as:

$$\text{Sinus severity score} = (\text{sinus mucosal volume}) / (\text{sinus mucosal volume} + \text{sinus air volume}) \times 100.$$

The sinus severity score and the change from baseline at all available time points will be calculated for patients in the PFAS.

3.5.6 Sinus CT: Zinreich score

In addition to the Lund-Mackay score described in Section 3.4.2, the same CT images will also be scored using the Zinreich (modified Lund-Mackay) scoring system ([Okushi et al 2013](#), [Likness et al 2014](#)).

All five sinuses (maxillary, anterior ethmoid, posterior ethmoid, sphenoid, and frontal) on each side will be scored based on the percentage of opacification from mucosal thickening according to [Table 8](#). Ostiomeatal complex has three categories: 0 - completely patent; 1 - partially obstructed, and 2 – completely obstructed. The maximum total Zinreich score is 50 (54 when including the Ostiomeatal complex score).

Only data from blinded central reader(s) will be used for analysis. The observed values and the changes from baseline at each time point will be calculated.

Table 8 Zinreich score

Score	Percent opacification
0	0%
1	1%-25%

2	26%-50%
3	51%-75%
4	76%-99%
5	100%

3.5.7 Short form 36-item health survey, version 2 (SF-36v2)

The short form 36-item health survey, version 2 (standard recall) (SF-36v2) is a 36-item, self-report survey of functional health and well-being, with 4-week recall period ([Quality Metric 2011](#)). Responses to 35 of the 36 items are used to compute an 8-domain profile of functional health and well-being scores. The remaining item, referred to as the ‘health transition’ item, asks patients to rate how their current state of health compared to their state of health 1 year ago, and is not used to calculate domain scores. The 8-domain profile consists of the following subscales: physical functioning (PF), role limitations due to physical health (RP), bodily pain (BP), general health perceptions (GH), vitality (VT), social functioning (SF), role limitations due to emotional problems (RE), and mental health (MH). Psychometrically based physical and mental health component summary scores (PCS and MCS, respectively) are computed from subscale scores to give a broader metric of physical and mental HRQL.

Categorical analyses will be conducted to evaluate treatment impact on the basis of the established threshold values for change for each scale. The SF-36v2 threshold listed in [Table 9](#) is suitable for interpreting change at the individual level and is referred to as the responder threshold or responder definition ([Quality Metric 2011](#)). SF-36 responders, defined as change \geq threshold noted in [Table 9](#), will be derived using the approach mentioned in [Section 3.1.5](#), regardless of surgery or SCS use for CRSwNP.

Table 9 Threshold values for the SF-36v2 scale and summary measures

	SF-36v2 score									
Threshold	PCS	MCS	PF	RP	BP	GH	VT	SF	RE	MH
Individual change	3.4	4.6	4.3	3.4	6.2	7.2	6.2	6.9	4.5	6.2

BP=Bodily Pain; GH=General Health Perceptions; MCS=Mental Health Component Summary; MH=Mental Health; PCS=Physical Component Summary; PF=Physical Functioning; RE=Emotional Problems; RP=Role Limitations due to Physical Health; SF=Social Functioning; VT=Vitality.

3.6 Pharmacokinetic and immunogenicity variables

According to the SoA [Table 2](#) and [Table 3](#) in the CSP, PK and ADA assessments will be collected during the DB period and the OLE period.

3.6.1 Pharmacokinetic variables

Serum samples for pharmacokinetic assessments will be collected according to visit schedule in [Table 2](#) and [Table 3](#) of the CSP. The drug concentration levels will be summarised using descriptive statistics.

3.6.2 Immunogenicity variables

Anti-drug antibodies (ADA) variables, such as ADA responses, will be generated and analysed as per the details in Appendix 8.7.

3.7 Exploratory efficacy variables

According to the SoA Table 2 and Table 3 in the CSP, exploratory efficacy assessments will be collected during the DB period only, except that asthma exacerbation will be further collected during the OLE period. Unless otherwise specified, derivation of relevant endpoints applies to the DB period and will be reported at the primary DBL. Additional data on asthma exacerbation from the OLE period will be reported at the final DBL.

3.7.1 Asthma control questionnaire 6

The ACQ-6 will be collected for patients in PFAS. Patients are asked to record their experience with 5 symptoms (night-time waking, symptoms on waking, activity limitation, shortness of breath, and wheezing) and use of short-acting β 2 agonist over the previous week using a 7-point scale (0= no impairment; 6=maximum impairment). The ACQ-6 score is calculated by taking the mean of the 6 equally weighted items and ranges from 0 (well controlled) to 6 (extremely poorly controlled).

Individual score change of at least -0.5 is considered clinically meaningful and is used to support the responder definition (Juniper et al 2005, Juniper et al 2006). An ACQ-6 responder at Week 56 will be defined as a patient who had improvement of at least 0.5 on ACQ-6, i.e., an ACQ-6 responder at Week 56 variable takes value 1 if change from baseline to Week 56 in ACQ-6 \leq -0.5 and 0 otherwise. ACQ-6 responder variables at Week 24 are similarly defined based on change from baseline to Week 24.

ACQ-6 responses at Week 24 and Week 56 will be derived based on the classifications below and the approach mentioned in Section 3.1.5, regardless of surgery or SCS use for CRSwNP.

- ACQ-6 (Timepoint– baseline) \leq -0.5 → Improvement
- $-0.5 <$ ACQ-6 (Timepoint– baseline) $<$ 0.5 → No change
- ACQ-6 (Timepoint– baseline) \geq 0.5 → Deterioration

Furthermore, patients will also be categorised according to their ACQ-6 using the following score thresholds (Juniper et al 2005, Juniper et al 2006) and the approach mentioned in Section 3.1.5, regardless of surgery or SCS use for CRSwNP.

- ACQ-6 (Timepoint) \leq 0.75 → Well controlled
- $0.75 <$ ACQ-6 (Timepoint) $<$ 1.5 → Partly controlled

- ACQ-6 (Timepoint) $\geq 1.5 \rightarrow$ Not well controlled

3.7.2 Asthma exacerbations rate (AER)

The number of exacerbations will be provided for 2 periods (i.e., DB period and OLE period as defined in Section 3.1.1), respectively. A patient will be considered as having asthma exacerbation if he/she starts a course of SCS (oral, parenteral) use due to asthma that lasts at least 3 days or have an emergency room/urgent care visit with SCS use due to asthma that lasts at least 3 days or a hospitalisation due to asthma.

The annual exacerbation rate in each treatment group will be calculated for DB period using the time-based approach by using the following formula:

Annual exacerbation rate = $365.25 \times$ total number of exacerbations / total duration of follow-up within the treatment group (days).

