8.1.1.6. Asthma exacerbations

Asthma exacerbation is defined by a worsening of asthma requiring:

- Use of systemic corticosteroids for at least 3 days; a single depo-injectable dose of corticosteroids will be considered equivalent to a 3-day course of systemic corticosteroids,
- An emergency room/urgent care visit (defined as evaluation and treatment for < 24 hours in an Emergency department or urgent care centre) due to asthma that required systemic corticosteroids (as per above),

- An inpatient hospitalization due to asthma (defined as an admission to an inpatient facility and/or evaluation and treatment in a healthcare facility for ≥ 24 hours),
- Use of systemic corticosteroids (oral, parenteral), an emergency room/urgent care visit or a hospitalisation due to asthma should be recorded in the corresponding eCRF. A hospitalisation should also be reported as an SAE.

The start date of an exacerbation is defined as the start date of systemic corticosteroid administration or date of hospital admission due to asthma. The end date of an exacerbation is defined as the last day of systemic corticosteroids or date of hospital discharge. A subsequent exacerbation must be preceded by at least 7 days in which neither criteria is fulfilled.

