6. CHANGES OF ANALYSIS FROM PROTOCOL

Not applicable.

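### The SAP's asthma exacerbation definition leaves out the protocol's depot-injection rule and its rules for separating events, and declares no change

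*SAP*

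**What the plan says.** Protocol 8.1.1.6 defines an exacerbation as a worsening of asthma that meets one of three criteria.

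- **Systemic corticosteroids (SCS) for three days or more.** The protocol adds that "a single depo-injectable dose of corticosteroids will be considered equivalent to a 3-day course of systemic corticosteroids".
- **An ER or urgent care visit** "due to asthma that required systemic corticosteroids (as per above"). The back-reference carries the depot rule over to these visits.
- **An inpatient admission for asthma.**

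It then dates the event: "The start date of an exacerbation is defined as the start date of systemic corticosteroid administration or date of hospital admission due to asthma". An event ends on the last SCS day or the discharge date. Events are separated by this rule: "A subsequent exacerbation must be preceded by at least 7 days in which neither criteria is fulfilled".

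SAP 3.7.2 keeps the three criteria. A patient counts "if he/she starts a course of SCS (oral, parenteral) use due to asthma that lasts at least 3 days", or for an "emergency room/urgent care visit with SCS use due to asthma that lasts at least 3 days or a hospitalisation due to asthma". Its annual rate is 365.25 times "total number of exacerbations / total duration of follow-up within the treatment group (days"). SAP 4.2.9.2 models the number of exacerbations per patient in the double-blind period with a negative binomial model. Neither section contains the depot rule, the dates or the separation rule.

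SAP 1.1 undertakes to describe any change from the protocol. The whole of SAP Section 6, which is reserved for such changes, reads "Not applicable".

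**The concern.** The two documents set different tests for the same event. A single depot dose passes the protocol's test by an explicit rule. Under the SAP it must meet a duration test, and nothing there says that it does.

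The second gap is of another kind. The SAP sentence says when a patient is considered to have had an exacerbation, but the analysis needs to know how many. Without dates and a separation rule, the SAP does not settle whether a steroid course followed within days by an admission is one event or two. Protocol 9.8 plans no adjudication committee, so the programmed definition decides the count.

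At stake are the double-blind rate and its treatment comparison, and the descriptive counts in the double-blind period and the open-label extension. If the definition is still open at unblinding, the choice of which events count is made with treatment known.

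**Working it through.** There is no planned figure to reproduce: neither document gives an exacerbation rate, a power statement or an event count. The check is a comparison of texts, followed by illustrative counting.

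**Step 1: side by side.**

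| Element | Protocol 8.1.1.6 | SAP 3.7.2 and 4.2.9.2 |
|---|---|---|
| SCS for three days or more | yes | yes |
| Single depot dose equals a 3-day course | yes | absent |
| ER/urgent care visit needs qualifying SCS | yes, by back-reference | yes, without the depot rule |
| Asthma admission | yes | yes |
| Start and end dates | yes | absent |
| 7 clear days before a new event | yes | absent |

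**Step 2: is either rule elsewhere in the SAP?** SAP 3.5.2 has a 7-day rule, but only for SCS courses given for CRSwNP. No other section supplies either rule for asthma exacerbations.

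**Step 3: made-up histories.** Clear days between contacts = next start − previous end − 1. The protocol count merges contacts with fewer than 7 clear days between them. The SAP count takes each qualifying contact as an event, which the text permits but does not prescribe.

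| History (study days) | Clear days | Protocol | SAP, literal |
|---|---|---|---|
| One depot injection, day 10 | none | 1 | 0 |
| SCS days 10–14 and 19–23 | 19 − 14 − 1 = 4 | 1 | 2 |
| Admission days 10–12, SCS days 15–19 | 15 − 12 − 1 = 2 | 1 | 2 |
| SCS days 10–14 and 35–39 | 35 − 14 − 1 = 20 | 2 | 2 |

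With the protocol's rules restored, the two counts agree in all four.

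**Step 4: size, on assumption only.** Let d be the share of protocol-defined events treated only with a depot dose, and s the number of extra split events per protocol event. Then SAP count / protocol count = 1 − d + s. The documents give neither quantity. Over an assumed range of 0 to 0.20 for each:

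- d = 0.20, s = 0: 1 − 0.20 + 0 = 0.80
- d = 0.10, s = 0.10: 1 − 0.10 + 0.10 = 1.00
- d = 0, s = 0.20: 1 − 0 + 0.20 = 1.20

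The definition does not alter follow-up time, so the annual rate scales by the same factor. The rate ratio between arms is multiplied by (1 − d + s) for benralizumab divided by (1 − d + s) for placebo. That is 1 if the factor is the same in both arms.

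**The case against.** The strongest reply is that the SAP is shorter than the protocol rather than opposed to it. SAP 1.1 presents the document as elaborating the protocol's analyses, and Section 6 declares no departure. A programmer could therefore take protocol 8.1.1.6 as still governing and apply it in full.

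That reply largely stands for event separation. A reader might infer that the SAP prescribes double counting; it does not. Its alternatives are joined by an or, and one episode can meet two of them and remain one exacerbation. The SAP leaves the matter unstated, and the counts of 2 above come from one reading of it.

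The reply is weaker for depot injections. It can be argued that a depot steroid acts for longer than a day; exclusion criterion 21 requires a 6-week washout for depot injections against 4 weeks for other SCS. But the SAP sentence names parenteral use and then sets a duration test on that use, and the protocol needed an express rule for a depot dose to pass the same test.

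Three other stronger readings are not supported.

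- **The three-day test at ER and urgent care visits is not a separate change.** The protocol's back-reference already imposes it; only the depot rule is lost.
- **No percentage error can be attached to the count.** The documents give no frequency of depot-only or closely spaced events.
- **A materially wider confidence interval is not shown.** If 10% of episodes were counted twice (an assumption), a Poisson count would have mean factor 0.9 × 1 + 0.1 × 2 = 1.1 and variance factor 0.9 × 1 + 0.1 × 4 = 1.3. Relative variance rises by 1.3 / 1.1² = 1.07, so the interval widens by about 4%, and by less with overdispersion.

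**Conclusion.** The point holds in a limited form. On depot injections the SAP states a test that, read literally, rejects events the protocol accepts, at ER and urgent care visits as well as outside them. On dates and separation the SAP is incomplete for the count that its own rate and model require. In both respects Section 6 declares nothing.

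It does not follow that exacerbations will be miscounted. That depends on the SAP being programmed literally, and on depot-only or closely spaced events occurring. The first gap lowers the count and the second can raise it, so they may cancel; size and net direction cannot be derived from the documents. The comparison between arms is distorted only if the net effect differs by arm.

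The endpoint is exploratory and outside the multiplicity procedure. The co-primary and key secondary endpoints, the sample size and the error control are unaffected. This is a minor correction, worth making because it is cheap and because it settles the definition before treatment is known.

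**What to change.** Before unblinding, amend SAP 3.7.2 to carry the three missing elements of protocol 8.1.1.6: the depot equivalence, applying also to ER and urgent care visits; the start and end dates; and at least 7 days with neither criterion met before a new exacerbation is counted. A cross-reference to protocol 8.1.1.6 would do as well. SAP 4.2.9.2 then needs no change, because it takes its definition from 3.7.2.

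For programming, SAP 3.5.2 already has a usable form: next start minus previous end greater than 7 is the same as next start − previous end − 1 ≥ 7, that is, at least 7 clear days.

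If the SAP's narrower wording is intended, state the difference and the reason in SAP Section 6 instead.

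The cost is a few sentences. It needs no new data item, no change to the model and no change to the sample size.
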